#### 8.2. PRIMARY ENDPOINT – ARM B (REVERSE SHOULDER ARthroPLASTY (RSA))

##### **Degenerative, rheumatoid or post-traumatic arthritis, and gross rotator cuff deficiency of the shoulder joint and proximal humerus fractures:**

The primary objective of the clinical investigation is to demonstrate non-inferiority of the ASES Shoulder Score at 24 months postoperative compared to the benchmark literature for Arm B. The 24 months mean ASES Shoulder Score result of the RFX System (RSA) will be compared to the pooled postoperative mean estimate of the control group (74.48 points). The pooled standard deviation of the postoperative ASES Shoulder Score result of the benchmark (11.08 points) was used to determine the lower limit. The lower maximum acceptable difference ( $-\theta$ ) is 63.40 points (mean of control -  $\theta$  or  $74.48 - 11.08 = 63.40$  points).

Based on the underlying distribution of the data and the result of the normality assessment, either the parametric one-sample t-test or the non-parametric one-sample sign test will be used to compare the 24 months postoperative ASES Shoulder Score results of the ReUnion RFX System (RSA) against the value of 63.40 points.

#### 8.3. SECONDARY ENDPOINTS (FOR BOTH ARM A AND B)

In addition to the principal endpoint, information on the following outcomes will be assessed up to 10 years after the index procedure:

- Safety: Incidence of device-related intraoperative and postoperative AEs
- Efficacy/Performance: Implant survivorship will be monitored

### **9. Selection of Clinical Investigation Population**

Subjects participating in this clinical investigation will be recruited from the investigator's standard patient population. Subjects will be enrolled onto the study by rolling enrollment until approximately 100 target patients are enrolled. All patients will be evaluated for clinical investigation participation based on the eligibility criteria listed below.

#### 9.1. INCLUSION CRITERIA

- Subject is willing to sign the informed consent.
- Subject is willing and able to comply with postoperative scheduled clinical evaluations.
- Subject is male or non-pregnant female and 18 years or older at the time of surgery.

d. When used with ReUnion TSA Humeral & Glenoid components as a Hemiarthroplasty or Total Shoulder Replacement, subject has one or more of the following:

- Aseptic necrosis of humeral head
- Painful, disabling joint disease of the shoulder resulting from degenerative arthritis, rheumatoid arthritis or post-traumatic arthritis
- Proximal humeral fracture and/or dislocation
- Clinical management problems where arthrodesis or alternative reconstructive techniques are less likely to achieve satisfactory results
- Previous unsuccessful total shoulder replacement, resurfacing or other procedure

e. When used with ReUnion RSA Humeral & Glenoid Components as a primary, fracture or revision total shoulder replacement, subject's joint has gross rotator cuff deficiency, a functional deltoid muscle and is anatomically and structurally suited to receive the implant, and subject has one or more of the following:

- Painful, disabling joint disease of the shoulder resulting from degenerative arthritis or rheumatoid arthritis
- Proximal humeral fracture
- Previously failed shoulder joint replacement

## 9.2. EXCLUSION CRITERIA

- Subject has an active or suspected latent infection in or about the shoulder joint.
- Subject has mental or neuromuscular disorder which would create an unacceptable risk of prosthesis instability, prosthesis fixation failure or complications in postoperative care.
- Subject has bone stock compromised by disease, infection or prior implantation which cannot provide adequate support and/or fixation to the prosthesis.
- Subject has anticipated activities which would impose high stresses on the prosthesis and its fixation.
- Subject is obese such that he/she produces a load on the prosthesis which can lead to failure of fixation of the device or to failure of the device itself.
- Subject has severe concomitant disease(s) which may significantly affect the clinical outcome.
- For Total Shoulder Arthroplasty and Hemiarthroplasty: Subject has absent, irreparable or non-functioning rotator cuff and other essential muscles.

## 9.3. WITHDRAWAL CRITERIA

If during the clinical investigation a subject must be prematurely withdrawn, then the procedures outlined in this section must be followed. These procedures should not interfere with the initiation of any new treatments that are necessary to treat a subject's condition. Information on all withdrawn subjects will be documented.

Subjects may be withdrawn from the clinical investigation for any of the following reasons:

- Subject Withdrawal: A subject may voluntarily withdraw from the clinical investigation at any time and for any reason. The subject should be asked when possible, and without any form of coercion, the reason for his/her decision. If the participant withdraws from the clinical investigation completely, then data collected up until the point of withdrawal will be included in the final analysis.

- ii. Lost to Follow-Up (LTFU): A subject will be considered LTFU after all reasonable efforts have been made to contact the subject and request his/her continued participation in the clinical investigation. All attempts to contact the subject must be documented and should include at least two attempts to contact the subject by phone and one attempt via a certified letter. Data collected up until the point where the subject is LTFU will be included in the final analysis.
- iii. Removal of Device or AE/Incident: The discontinuation of a subject's participation in the clinical investigation due to the removal of the ReUnion RFX System or AE/incident that prohibits his/her continued participation must be fully explained. All available information concerning the removal of the device or AE/incident should be provided. Data collected up until the point of removal or AE/incident will be included in the final analysis.
- iv. Death: The discontinuation of a subject's participation in the clinical investigation due to death must be fully explained. All available information concerning the death or AE should be provided. Removal of a subject from continued follow-up in the clinical investigation due to death will not be considered a device failure unless the death is directly caused by, or attributable to, the ReUnion RFX System. Data collected up until the point of death will be included in the final analysis.
- v. Other: A subject may be withdrawn by the investigator if he/she believes it is in the best interest of the subject, or if it is determined by the IRB that a subject's continued participation in the clinical investigation represents an unacceptable risk to the subject. The Sponsor must be notified immediately if this occurs. All data collected up until the point of withdrawal or IRB determination will be included in the final analysis. A subject may also be withdrawn if the subject is non-compliant with the clinical investigation procedures or visits, or if a selection criteria violation is noted after the subject received the clinical investigation treatment and it is determined that the subject should be discontinued. All data collected up until the point of withdrawal will be included in the final analysis.

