#### 10.4. SCHEDULE OF EVENTS

Assessment	Pre-Operative	Operative/ Discharge	6 Weeks a, b (+/- 2 weeks)	6 Months a, b (+/- 3 weeks)	12 Months a, b (+/- 4 weeks)	24 Months a, b (+/- 4 weeks)	Annually b (+/- 4 weeks)
Informed Consent	X						
Demographics & Medical History	X						
Inclusion/Exclusion	X						
Physical Exam	X		X c	X c	X c	X c	X c
Surgical Procedure		X					
ASES Shoulder Score	X		X d	X d	X d	X d	X d
Image Evaluation e, f	X	X	X	X	X	X	X
Subject Disposition g			X	X	X	X	X
	Device-Related AEs/Incidents & Reoperations will be collected throughout the course of the clinical investigation.						
	
 
a. Follow-up visit schedule to reflect Institution's Standard of Care practices
 
b. If the subject misses a visit and is outside of the visit window, then every effort should be made to collect data instead of noting visit as missed. Visit windows are calculated from index event, and not from previous visit.
 
c. Evaluation may be collected when subject presents in-clinic for study visit.
 
d. Evaluation can be collected via phone.
 
e. Radiograph collection should follow Institution's Standard of Care practices and no additional x-rays should be made for study purposes.
 
f. CT scans may be collected if part of Institution's Standard of Care practices.
 
g. Subject Disposition assessment will occur at any time point for subject withdrawal prior to the completion of the clinical investigation.
 
						

Table 1: Schedule of Events

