### 13.3. RELATIONSHIP TO THE DEVICE

Only events considered possibly, probably or definitely related to the device will be captured for this clinical investigation.

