6.7.3. Reoperation Surgery

For analysis of the time to the reoperation, the Kaplan-Meier method will be used. The times between surgery and the most recent or last available assessment per subject will be used together with the times between surgery and the date of reoperation (earliest reoperation in case that one subject experienced more than one reoperation). This analysis is part of the final report.

Evaluation Variable / Question	Level of Measurement	Recode and Analysis Plan
Adverse Events / Reoperation Surgery		
Creation of variable Difference between Date of Surgery [dd.mm.yyyy] and Date of First Reoperation [dd.mm.yyyy] in days (Variable(s): VISITDT)	Quantitative, ratio	Case summary with number and percentage of valid cases/values, missing cases/values (if any) and total cases/values. Mean, median, interquartile range, maximum, minimum, standard deviation, 95% confidence interval for mean, Shapiro-Wilk Test.
Creation of variable Difference between Date of Surgery [dd.mm.yyyy] and Date of “most recent” Visit [dd.mm.yyyy] in days (Variable(s): VISITDT)	Quantitative, ratio	N/A (Analyzed above), used for survivorship
Create new variable “Grouping variable – First Reoperation” (Variable(s): VISITDT)	Qualitative, nominal	- censored = survivors - events = first (earliest) Reoperation
Create new variable “Combined Time – First Reoperation” (Variable(s): VISITDT)	Quantitative, ratio	- Use time between surgery and most recent visit for surviving subjects - Use time between surgery and first reoperation for subjects with reoperation(s)
Use variables “Combined Time – First Reoperation” and “Grouping variable – First Reoperation”	Qualitative, nominal Quantitative, ratio	Case summary with number and percentage of valid cases/values, missing cases/values (if any) and total cases/values. Kaplan-Meier survival analysis: subject ID, time, status, cumulative proportion, Kaplan-Meier estimate, standard error of KM estimate, number of cumulative events, number of remaining cases, mean for survival time with 95% confidence interval, survival graph, hazard graph.

Table 6.7.3: All Assessments – Revision Surgery Tables List

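### Subjects withdrawn for an AE/incident are censored as survivors in the reoperation curve, so freedom from reoperation may be overstated if their later risk is higher

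*Protocol*

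**What the plan says.** - **Withdrawal.** Protocol 9.3 iii covers two reasons in one item: removal of the device, and an "AE/incident that prohibits his/her continued participation must be fully explained". The data rule is "Data collected up until the point of removal or AE/incident will be included in the final analysis". The item also asks that "All available information concerning the removal of the device or AE/incident should be provided", but sets no check on reoperation after the subject has left.
- **Collection.** Protocol 10.4 states that "Device-Related AEs/Incidents & Reoperations will be collected throughout the course of the clinical investigation". It does not say whether this extends to subjects already withdrawn.
- **Which AEs are recorded.** Protocol 13.3: "Only events considered possibly, probably or definitely related to the device will be captured for this clinical investigation".
- **Reoperation curve.** SAP 6.7.3 has two states. The event is the first reoperation. Everyone else is "censored = survivors", with the time rule "Use time between surgery and most recent visit for surviving subjects". There is no separate status for withdrawal because of an AE/incident.
- **Endpoint.** Protocol 8.3 lists, over 10 years, "Efficacy/Performance: Implant survivorship will be monitored". The SAP gives this endpoint no event definition of its own. Time to reoperation is the closest analysis, and Protocol 14 counts implant removal, and also irrigation and debridement, as reoperations.
- **Missing data.** Protocol 11.4 and SAP 4.6 provide only for reporting counts and percentages of missing cases.

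**The concern.** Kaplan-Meier estimation assumes that a censored subject has the same later risk as the subjects still under observation at that time. Someone who left because of loosening, dislocation or deep infection may well not. If the reoperation takes place after the subject has left, nothing in the plan ensures that it is recorded, and the subject stays in the curve as a survivor.

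At stake is the 10-year freedom-from-reoperation figure, which a reader will take as evidence on implant survivorship. Once contact has ended, reoperation status may be hard to recover, so the matter is best settled in the plan.

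**Working it through.** **Is there a figure to reproduce?** No. The documents state no expected survivorship, reoperation rate or number of AE/incident withdrawals. The 56% drop-out in the sample-size sections is not broken down by reason. All inputs below are therefore assumptions.

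**Step 1: path of one subject under the rules as written.**
1. A subject has an AE/incident that prevents continued participation, and leaves under 9.3 iii.
2. Data enter the analysis up to that point only.
3. No reoperation is on record, so SAP 6.7.3 assigns the censored state.
4. Time ends at the most recent visit, which may fall before the AE itself.
5. A later reoperation has no planned route into the data set.

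**Step 2: small illustration (assumed).** Take 50 subjects implanted in one arm, recorded reoperations at months 3, 8 and 18, and AE/incident withdrawals at months 6, 9 and 12. Numbers at risk at the three events are 50, 48 and 45.

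Planned estimate at month 18: 49/50 × 47/48 × 44/45 = 0.938.

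Suppose instead that all 50 are followed to month 18 and *k* of the three withdrawn subjects are reoperated by then. Freedom from reoperation is (50 − 3 − k)/50:

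| k | Full follow-up | Planned curve |
|---|---|---|
| 0 | 47/50 = 94.0% | 93.8% |
| 1 | 46/50 = 92.0% | 93.8% |
| 2 | 45/50 = 90.0% | 93.8% |
| 3 | 44/50 = 88.0% | 93.8% |

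The gap runs from −0.2 to +5.8 points and depends wholly on *k*. If the withdrawn subjects carry only the same risk as the others, the censoring is not informative and 93.8% stands.

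For other numbers of withdrawals, taking all withdrawn subjects as later reoperated (the extreme case):
- Two withdrawals (one before month 8): 49/50 × 47/48 × 45/46 = 93.9%, against 45/50 = 90.0%.
- Four withdrawals (one before month 8): 49/50 × 47/48 × 43/44 = 93.8%, against 43/50 = 86.0%.

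**Step 3: ten-year horizon (assumed).** Let S be the true 10-year freedom from reoperation under a constant hazard, and q the share of first reoperations that follow an AE/incident withdrawal and go unrecorded. Only a fraction 1 − q of the hazard is seen, so the planned curve tends to S^(1−q).

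| S | q = 0 | q = 10% | q = 25% | q = 50% |
|---|---|---|---|---|
| 95% | 95.0% | 95.5% | 96.2% | 97.5% |
| 90% | 90.0% | 91.0% | 92.4% | 94.9% |
| 85% | 85.0% | 86.4% | 88.5% | 92.2% |

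For example, 0.90^0.75 = 0.924, an excess of 2.4 points. A simulation of 400,000 subjects, with these withdrawals censored at the last scheduled visit, agrees to within about 0.15 points. It gives an excess of about 0.4 to 7.1 points where q is above zero. Adding 56% non-informative drop-out hardly changes it.

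**The case against.** The case against is substantial, and most of it limits how far the point can be taken.

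- **Few subjects may be affected.** The clause applies only when the AE/incident prevents participation. Protocol 11.3.2 continues annual ASES collection until all components have been removed, so partly revised subjects stay in, and Protocol 10.4 allows the score by phone. A subject with loosening who stays and is then revised is counted correctly. This stands.
- **A reader might infer that those withdrawn are the patients nearest to revision.** The documents do not show it. Section 13.3 limits which AEs are recorded, not which AEs may trigger 9.3 iii, so an unrelated illness could qualify. Foreseeable events in 13.5 include deep vein thrombosis and pulmonary embolism. A subject too ill for surgery could have a lower reoperation risk.
- **A reader might infer that every later reoperation is lost.** That is too strong. Section 9.3 iii asks for available information, its data sentence does not forbid later collection, and the AE form has fields for surgical action, resolution and outcome (SAP 6.1, not reported). What stands is that follow-up after withdrawal is unspecified.
- **The AE is not lost.** A recorded device-related AE is an event in the time-to-first-AE curve (SAP 6.6). That does not correct the reoperation curve.
- **Other features act the other way on implant survivorship.** Any reoperation counts as an event, including irrigation and debridement. Deaths without reoperation would be censored under the two-state rule, where a competing-risk approach would give a higher survivorship figure. The net error in implant survivorship therefore has no fixed sign.

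**Conclusion.** The point holds in conditional form. The data cut-off in Protocol 9.3 iii and the two-state rule in SAP 6.7.3 together censor AE/incident withdrawals as survivors, and no planned analysis tests the effect. If these subjects have a higher later reoperation risk than those still followed, freedom from reoperation may be overstated.

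The size cannot be taken from the documents. In the 50-subject illustration the gap runs from none to 5.8 points. Over the assumed 10-year range it runs from zero to about 7 points. Both rest on assumed event rates, and on assumed later reoperations among the withdrawn.

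It would be tempting to say that survivorship is overstated, or that the error always favours the device. The documents support neither: they give no count of such withdrawals and no later reoperation rate.

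The removal half of 9.3 iii is a matter of clarification. Removal is a reoperation under Protocol 14 and so should be an event, but a cut-off at the point of removal leaves open whether the removal itself is included.

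**What to change.** 1. **Protocol 9.3 iii.** Separate the end of study visits from the end of data collection. Unless consent is withdrawn, keep recording reoperation, removal and vital status from routine records or by phone. State that the removal itself is part of the data. This concerns data collection only, not when a subject should be withdrawn.
2. **SAP 6.7.3, main curve.** Count a withdrawal with device removal as its primary reason (PRIMRSN) as an event.
3. **SAP 6.7.3, sensitivity curve.** Prespecify a second curve in which withdrawals for a device-related AE/incident without a recorded reoperation count as events, with the event date fixed in advance. Report it beside the planned curve as a conservative analysis for this withdrawal reason. It is not an overall lower bound, because voluntary withdrawals and losses to follow-up stay censored.

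PRIMRSN is already listed in SAP 5.3 and used for mortality in SAP 6.7.2. Its answer options are not shown. If they follow 9.3, where removal and AE/incident share one item, they need to be split.

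The cost is wording in both documents, slightly more site follow-up, and a sensitivity figure that may be less favourable.

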### **10.3. FOLLOW-UP EVALUATIONS**

Subjects in this clinical investigation will be evaluated at Preoperative, Operative/Discharge, and at 6 Weeks (4 weeks – 8 weeks), 6 Months (24 weeks – 28 weeks), 12 Months (48 weeks- 56 weeks), 24 Months (100 – 108 weeks) and annually thereafter. The follow-up evaluations will include assessment of device-related AEs/incidents, radiographs and ASES Shoulder Score.

Investigative site personnel will contact subjects prior to their scheduled follow-up evaluations to encourage compliance with clinical investigation visits and participation.

If a subject misses a visit and is outside of the visit window, every effort should be made to collect data instead of noting the visit as missed.

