## 11.2. ANALYSIS POPULATIONS

It is expected during this clinical investigation only one population for ReUnion RFX System per arm will exist and all subjects will be analyzed “Per Protocol” (PP). However, it cannot be fully avoided that in theory subjects might need to be excluded from the PP population. In this occasion, there will be two groups being fully analyzed to ensure transparency and avoid bias.

The groups are defined as follows:

- **Intent-to Treat Population**

The Intent-to-Treat (ITT) Population is defined to be all enrolled subjects. An enrolled subject is a subject that has signed informed consent, all screening procedures have been successfully completed, is eligible and can receive treatment. The ITT population will not be analyzed for the annual reports and will only be included in the final report.

- **Per Protocol Population**

The PP Population is defined to be all subjects in the ITT Population with no major protocol violations. The protocol deviations that will exclude a subject are as follows:

- The subject does not receive the ReUnion RFX System

- The subject does not meet all eligibility criteria
- The subject has a protocol deviation that is considered likely to affect subject outcomes.

After the clinical investigation has been completed, a review of the data will be conducted to determine which subjects are to be excluded from the PP population.

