### 11.3.2. Primary Analysis / Endpoint

The objective of the clinical investigation is to demonstrate the non-inferiority (equal or better) of the ASES Shoulder Score in relationship to the officially cleared indications in comparison to respective clinical outcome data in the scientific literature.

Data collection of ASES Shoulder Score will be collected according to the schedule in Table 1, Schedule of Events. This will be repeated annually in all subjects who have the prosthesis with full or partial implant survival (including all subjects without removal of all endo-prosthesis components).

The 24 months postoperative results for subjects implanted with ReUnion RFX System will be compared to a historical group and results reported by respective clinical outcome data in the scientific literature.

[figure not shown]
Higher ASES Shoulder Score results are linked to better subject results and vice versa.

The clinical investigation endpoint is non-inferiority to the control, meaning the clinical investigation result should be equal or better than the control. In this clinical investigation, an equal or better ASES Shoulder Score result means equal or more ( $\geq$ ). As only results from samples will be captured, results are mostly estimates of the true population parameter. These

estimates vary by a certain area, where it is expected that the true population parameter falls within. Based on this, it is required to specify a lower limit for the acceptable difference or zone of indifference, denoted as  $-\theta$ .

Hypotheses are developed to allow for a comparison of the 24 months postoperative ASES Shoulder Score effectiveness/performance between the two underlying populations. The 24 months post-operative ASES Shoulder Score is the primary endpoint of this clinical investigation. Hypothesis tests will be one-sided with a significance level  $\alpha$  of 5%.

[figure not shown]
Table 3a: Arm A (TSA/HA)

Hypothesis	Equations	Interpretation
Null ( $H_0$ )	$A - B < -\theta$	Central tendency of A is inferior to the central tendency of B.
	ReUnion RFX System (TSA/HA) – Control (Benchmark) $< -\theta$	
Alternative ( $H_1$ )	$A - B \geq -\theta$	Central tendency of A is non-inferior to the central tendency of B.
	ReUnion RFX System (TSA/HA) – Control (Benchmark) $\geq -\theta$	
		
Possible Evidence (p)	Possible Decisions	Possible Conclusions – ASES score

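### Section 9.3(v) allows an implanted subject to be withdrawn for non-compliance or a late-found eligibility violation, which ends data collection that the 24-month and 10-year endpoints still need

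*Protocol*

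**What the plan says.** Protocol 9.3(v) first covers withdrawal by the investigator in the subject's interest, or on an IRB determination of unacceptable risk. It then adds two administrative grounds. The first is "A subject may also be withdrawn if the subject is non-compliant with the clinical investigation procedures or visits". The second applies "if a selection criteria violation is noted after the subject received the clinical investigation treatment" and a decision is made to discontinue that subject. It sets no threshold for non-compliance and does not say who decides, or when. On data it says: "All data collected up until the point of withdrawal will be included in the final analysis". Nothing provides for collection afterwards.

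Other sections assume that collection goes on:

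- **8.3**, on device-related adverse events and implant survivorship: "information on the following outcomes will be assessed up to 10 years after the index procedure".
- **11.3.2**, on ASES: "This will be repeated annually in all subjects who have the prosthesis with full or partial implant survival".
- **10.3**, and Table 1 note b in 10.4, on a missed visit: "every effort should be made to collect data instead of noting the visit as missed".
- **11.2** (and SAP 5.1): subjects who fail an eligibility criterion are left out of the per-protocol (PP) population. "The Intent-to-Treat (ITT) Population is defined to be all enrolled subjects", but the next sentence defines an enrolled subject as one who is, among other things, eligible.

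**The concern.** In a drug trial, a withdrawal rule may serve to stop treatment. Here the device is already implanted, so withdrawal on these two grounds stops only the measurement of how it performs. The analysis does not need the rule, because 11.2 already has a way to deal with ineligible subjects.

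The study is unblinded and the decision is discretionary. It could therefore be taken when a subject's early course is known. Several exclusion criteria in 9.2 concern instability, inadequate fixation or device failure, so subjects found to violate those criteria may well carry a higher risk. If they leave observation, device-related events and reoperations may be under-counted, and an ITT analysis of the 24-month score would lack values that could have been obtained.

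**Working it through.** **1. The plan's own figure.** Sections 11.1.1 and 11.1.2 state 80.3% power with 10 cases. The effect size is 20.33/20.33 = 11.08/11.08 = 1.00. A two-sided one-sample t-test at 5% with n = 10 (noncentral t, noncentrality √10) gives 80.3%, so the figure reproduces in both arms. This point does not change it.

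**2. What is lost, by time of withdrawal.** Years of follow-up lost = 10 − t.

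| Withdrawal | 24-month ASES | Safety follow-up lost |
|---|---|---|
| Soon after surgery | lost | close to 10 years |
| At 1 year | lost | 9 years |
| Just after the 24-month visit | kept | up to 8 years |

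**3. Whether a later step repairs it.** Protocol 11.4 and SAP 4.6 only count missing values. The Kaplan-Meier analyses (SAP Tables 6.6.2 and 6.7.3) use time to the most recent visit for subjects without an event, so a withdrawn subject is censored there. That is harmless only if withdrawal is unrelated to risk.

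**4. Which analyses are affected.**

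| Subject | PP primary test | ITT | Safety and survivorship |
|---|---|---|---|
| Found ineligible | no effect: excluded from PP anyway | affected if ITT includes the subject, which the definition leaves unclear | affected |
| Non-compliant, stays in PP | affected if withdrawn before 24 months | affected | affected |

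**5. Illustrative size for the 24-month score.** The documents give no rate for these withdrawals, so the inputs are assumptions: a fraction f = 5–10% withdrawn before 24 months, who would score d = 10–15 points below the rest, with 20 evaluable subjects in the arm before withdrawal.

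If the mean over all implanted subjects is μ, the mean in those retained is μ + f × d. The bias is 0.05 × 10 = 0.5 to 0.10 × 15 = 1.5 points. As a share of the allowed difference, that is 4.5–13.5% in Arm B (11.08 points) and 2.5–7.4% in Arm A (20.33 points).

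Now put μ exactly at the limit (63.40 or 38.41) and use the one-sided 5% t-test of 11.3.2 with the benchmark SD. The noncentrality is f × d × √n / SD, where n is the number retained.

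| Arm (SD) | f, d | n retained | Noncentrality | Type I error |
|---|---|---|---|---|
| B (11.08) | 5%, 10 | 19 | 0.5 × √19 / 11.08 = 0.197 | 7.3% |
| B (11.08) | 10%, 15 | 18 | 1.5 × √18 / 11.08 = 0.574 | 13.7% |
| A (20.33) | 5%, 10 | 19 | 0.5 × √19 / 20.33 = 0.107 | 6.2% |
| A (20.33) | 10%, 15 | 18 | 1.5 × √18 / 20.33 = 0.313 | about 9% |

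A larger arm raises these values because the bias does not shrink with n. As an extreme, 44 evaluable in one arm (100 × 0.44, with every subject in that arm) gives 8.7–21% in Arm B and 6.8–11.7% in Arm A.

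**6. Illustrative size for device events.** If withdrawn subjects have r times the event risk and none of their events is seen, incidence among those retained, relative to the truth, is 1 / ((1 − f) + f × r). For f = 5%, r = 2 this is 1/1.05 = 95%. For f = 10%, r = 3 it is 1/1.20 = 83%. Again f and r are assumptions.

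**The case against.** Several stronger readings are tempting, and the documents do not support them.

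- **That data are discarded.** They are not. Section 9.3(v) keeps everything collected before withdrawal, so a poor 24-month score already recorded cannot be removed by a later withdrawal.
- **That the withdrawn are the subjects most likely to do badly.** This is inference. Section 9.2 makes it plausible for violations that concern fixation or device failure. It says nothing of the kind for non-compliant subjects, or for violations of criteria such as age.
- **That late-found ineligibility inflates the PP primary test.** It cannot, because 11.2 removes these subjects from PP whether or not their score exists. The figures in step 5 apply to ITT, or to non-compliant subjects who stay in PP.
- **That ITT would otherwise hold every implanted subject.** Read literally, the definition of an enrolled subject requires eligibility, so scores from ineligible subjects might enter no population even if collected.
- **That 9.3(v) flatly contradicts 10.3.** Chasing a missed visit and having an end point for persistent non-compliance can coexist, and the word used is non-compliant. The two sit poorly together, however: 9.3(ii) asks for at least two telephone attempts and a certified letter before a subject counts as lost, while the non-compliance ground asks for no contact attempt.

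It is also fair to say that withdrawals are documented (9.3) and tabulated with reasons, by site and visit and for each arm (SAP 5.3). The loss would be visible. It would not be corrected.

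**Conclusion.** The point holds in a limited form. Section 9.3(v) permits observation of an implanted subject to end on two administrative grounds. That conflicts with the 10-year assessment in 8.3 and the annual ASES in 11.3.2, and no later analysis makes up for it. The main effect is on device-related events and survivorship, and on any ITT analysis; the PP primary test is exposed only through non-compliant subjects who remain in it.

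The size is unknown. The ranges of about 7–14% (Arm B) and 6–9% (Arm A) are illustrations. They assume 5–10% withdrawn before 24 months, a 10–15 point deficit, 20 evaluable subjects, the benchmark SD, use of the t-test and a true mean exactly at the limit. With no difference between withdrawn and retained subjects, the score bias is zero and the loss is one of information only. The change is worth making because it is cheap, not because serious bias has been shown.

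**What to change.** In protocol 9.3(v), replace the two grounds with text such as:

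> A subject with valid consent who has received the ReUnion RFX System is not withdrawn from follow-up for a selection-criteria violation or non-compliance. The deviation is recorded, PP status is set under 11.2, and ASES, device-related AEs and reoperations continue to be collected unless the subject withdraws consent or is lost to follow-up under 9.3(ii).

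Keep withdrawal by the subject, and by the investigator or the IRB in the subject's interest. The condition of valid consent is needed because consent is itself an inclusion criterion, and a subject whose consent was missing or invalid from the start must not be held in follow-up by this rule.

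In protocol 11.2 and SAP 5.1, state that implanted subjects later found ineligible remain in ITT and in the safety and survivorship analyses. Without this, the extra data might belong to no population.

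The cost is one paragraph in 9.3, a sentence in each of 11.2 and SAP 5.1, and a little more follow-up work for sites. Table 1 note d already allows ASES to be collected by telephone. Sample size and stated power do not change.
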